10.0 COST-EFFECTIVENESS STUDY PROCEDURES (AIM 2, R61)

10.1 Overall Approach

We will build a decision model to estimate and compare the budget impact, cost-effectiveness, and population outcomes of our multilevel PrEP intervention. We will model the value of each component (PrEP navigator, HMP app, telehealth provider) as assessed in Aim 1, separately and in combination. We will examine the impact of alternative combinations via sensitivity analyses, varying assumptions about the costs and combined effectiveness of the interventions. We will further parameterize the model and conduct sensitivity analyses using published PrEP cost and effectiveness data⁵³⁻⁵⁶.

We will directly measure costs and a surrogate marker of HIV prevention effectiveness (PrEP uptake) in our RCT. Our analysis presumes that increasing uptake of PrEP is a desired outcome, focusing our assessment on incremental STI clinic related intervention costs. Following established methods, we will measure non-research related costs associated with the intervention and control arms to estimate incremental cost per additional person starting PrEP. Analyses will take the perspective of the STI clinics and public payers.

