| 
[name], MPH Co-Investigator Professor, College of Nursing Florida State University [name] Email: [contact]
 | 
[name], MPH Program Officer Clinical Prevention Research Branch Prevention Sciences Program Division of AIDS National Institute of Allergy and Infectious Diseases [name] [name] 20892-9831 United States Email: [contact]
 |

| Study staff | |
|---|--|
| [name] Study Coordinator Institute for Global Health & Infectious Diseases, UNC-Chapel Hill Bioinformatics Building, 2 nd floor [name] Email: [contact] | |

[figure not shown]
Study Synopsis

| | |
|------------------------------|--|
| SPONSOR: | National Institute of Allergy and Infectious Diseases (NIAID) |
| TITLE OF STUDY: | Meet me where I am: A multilevel strategy to increase pre-exposure prophylaxis (PrEP) uptake and persistence in rural North Carolina (NC). |
| PROTOCOL NUMBER: | UNC IRB: 22-3058, IGHID 12221 NIH Grant: R61AI174285 |
| STUDY DESIGN AND CONDITIONS: | 
This project consists of two phases to be completed over five years. Phase 1 (Aims 1 and 2) will be completed during Years 1-3 (R61). The Phase 1 study is a randomized trial of a multilevel PrEP intervention strategy in rural NC sexually transmitted infection (STI) clinics, with primary outcome of PrEP uptake within 3 months of an index STI clinic visit.
 
Participants will be randomized 1:1 to an intervention or control condition. Participants enrolled in the intervention arm will receive a multilevel intervention with three components: a PrEP Navigator to facilitate linkage to PrEP services and completion of applications for health insurance/drug assistance; a Digital Health Intervention (DHI) platform (HealthMpowerment) – a HIPAA-compliant evidence-based DHI that provides interactive educational resources, social support, and tools for developing PrEP behavioral skills and self-efficacy; and referral to Telehealth PrEP services as an option for linking to PrEP care.
 
Control arm participants will receive the standard PrEP referral services available in a given clinic setting. They will also receive linkage to a limited version of the DHI, with basic PrEP resources and information.
 
The current protocol is for the Phase 1 study.
 |
| DURATION: | The navigation intervention period is 3-6 months (dependent on enrollment date), enrolled study participants are followed for up to 12 months . |

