| HMP app (participant-facing) | |
| Study timeline and calendar | Displays access to upcoming study-related activities and a two-way secure messaging feature for communication between participants and research staff (including PrEP navigator) and receive reminders to promote completion |
| Resource Center | Expansive library of multi-media content tailored for YGSM populations of varying developmental stages |
| Activities | Information/skills building (quizzes, self-assessments, goal setting, choose-your-own-adventure, etc.) |
| Newsfeed | Social component provides space for user-generated content to include peer-to-peer sharing, exchange of health information and narrative discussions on topics of interest |
| Ask the Expert | Allows participants to ask questions to HIV/PrEP care expert provider and receive answers |
| Medication Tracker | Self-monitor PrEP adherence with visual calendar and provision of user feedback |
| Health Tracker | Self-monitor behaviors that impact PrEP adherence with reminders and provision of tailored feedback |
| Gamification | Sophisticated tracking of app use to trigger behavior-specific virtual rewards (e.g. badges) |

Telehealth PrEP referral: PrEP Navigators can link interested participants to telehealth PrEP via self-referral. The study facilitates referral for intervention arm participants to pre-existing telehealth PrEP services. The telehealth PrEP services participants receive are not provided, financed, or staffed by the study. Participants will receive telehealth PrEP services via the technology platform or service that the provider typically employs. PrEP clinical eligibility, visit frequency, monitoring labs, and all other PrEP management will be at the discretion of the established PrEP provider. Study staff will access records for participants who have agreed to medical record release. PrEP navigators can assist with appointment scheduling, reminders, and other provider-access issues, as requested, for the period of navigation service receipt.

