3.2.2 Control Arm Condition

All control arm activities may be conducted virtually.

Participants randomized to the control arm will receive:

Digital Health Intervention Standard-of-Care: The control arm version of the HealthMPowerment DHI platform includes Study timeline and Calendar features and all educational content in the Resource Center.

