6.3 Intervention Procedures

Intervention arm participants will have access to the three primary intervention components (PrEP Navigation, Digital Health Intervention, and Telehealth PrEP Referral) for the full duration of the 6-month follow-up period, limited to 3-months for a subset of participants enrolled in approximately the final quarter of enrollment. Participants will be encouraged to use the intervention features through a combination of study staff reminders, PrEP navigator interactions, automated in-app notifications, and automated SMS and push notifications.

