Sensitivity analyses examine the potential impact of varying cost and effectiveness assumptions. We will employ deterministic sensitivity analyses to examine model assumptions and key parameter uncertainties. We will assume that intervention effects would be additive unless cost components are redundant. We will conduct probabilistic sensitivity analyses (using Monte Carlo simulation x5000) to account for parameter uncertainty⁶⁵, capturing input uncertainty (e.g., PrEP effectiveness, intervention cost and effectiveness). Upper and lower bounds will be based on trial data, literature, and/or expert opinion. Results represent an average across simulated model runs with an estimated uncertainty range. We will depict sensitivity results graphically and with relevant descriptive statistics. We will estimate net monetary benefits over a range of willingness-to-pay thresholds¹⁵⁵⁻¹⁵⁹, depicting the probability that each intervention is preferred given the decision maker is willing to pay at least the threshold value for each additional person started on PrEP or each QALY gained^{63,64,66,67}.

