10.5 Dissemination

We will generate an interactive interface with data customized for each HD, to be used by decision makers to guide scale-up of the multilevel PrEP intervention. Such an interface augments conventional population health modeling data, allowing stakeholders to make informed decisions specific to their population and setting. By integrating cost-effectiveness and budget impact results from each intervention component (PrEP navigator, telehealth PrEP, and digital health platform) into a single interactive tool, decision makers will be able to access a side-by-side comparison of cost and impact estimates specific to their context. Examples of modifiable parameters include: population size, HIV incidence, budget and intervention effectiveness. Decision support tool outputs will include estimated: cost of each component of study intervention implementation (PrEP navigator, telehealth PrEP, digital health platform), cost per person starting PrEP and impact of implementation on number of people starting PrEP. We will work with local partners to make the customizable platform widely available.

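### Aim 2 promises component-level value as assessed in Aim 1, but a two-arm trial of one bundle identifies only the package effect

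*Combined protocol and SAP*

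**What the plan says.** **Trial design.** The Study Synopsis states: "Participants will be randomized 1:1 to an intervention or control condition". Section 6.3 describes what the intervention arm is offered: "Intervention arm participants will have access to the three primary intervention components (PrEP Navigation, Digital Health Intervention, and Telehealth PrEP Referral"). Section 3.2.2 gives controls a reduced app: "The control arm version of the HealthMPowerment DHI platform includes Study timeline and Calendar features and all educational content in the Resource Center". The only effectiveness contrast in 9.2.1 is intervention against control. On how telehealth is reached, 3.2.1 says "PrEP Navigators can link interested participants to telehealth PrEP via self-referral".

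**Aim 2 model.** Section 10.1 promises: "We will model the value of each component (PrEP navigator, HMP app, telehealth provider) as assessed in Aim 1, separately and in combination". Section 10.3 places the randomised arm at the first decision node and takes the event probabilities from trial data. In the sensitivity-analysis paragraph of 10.4 the plan adds: "We will assume that intervention effects would be additive unless cost components are redundant". Section 10.5 describes "integrating cost-effectiveness and budget impact results from each intervention component (PrEP navigator, telehealth PrEP, and digital health platform) into a single interactive tool", so that decision makers can compare cost and impact estimates side by side.

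**The concern.** The plan attributes to Aim 1 something that Aim 1 does not measure. No randomised group receives one component without the others, so the trial yields one effect, that of the package. Even for the app, the arms differ by full versus limited version, and that difference always comes together with navigation and telehealth referral.

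At stake is how Aim 2 results are read. A health department using the tool could keep or drop a component on a cost-effectiveness figure that appears to come from a randomised trial but rests on an assumed division of the package effect. An even division would not be a neutral default. The effect-size rationale in 9.1 cites a pilot app without navigation that showed no difference between arms. It also cites a demonstration project with 48.5% linkage among navigation users against 2.8% among non-users. Neither is offered as a model input, and the second is not a randomised comparison, but both suggest that contributions may be very unequal.

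**Working it through.** The plan states no component-level effect, so there is no figure of its own to reproduce. The check is whether the design can identify one.

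**Inputs.** Two arms (Study Synopsis); all three components offered together (6.3); limited app for controls (3.2.2); planning values of 2.5% control uptake and a 7.5-point gain (9.1).

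**Step 1: additive model.** Let N, D and T mark navigator, full rather than limited app, and telehealth referral:

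uptake = b0 + bN·N + bD·D + bT·T

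- Control, (N, D, T) = (0, 0, 0): uptake = b0
- Intervention, (1, 1, 1): uptake = b0 + bN + bD + bT

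The design matrix has rows (1,0,0,0) and (1,1,1,1). Its rank is 2, against 4 unknowns. Only b0 and the sum bN + bD + bT can be estimated. With all interactions there are 8 unknowns and the rank is still 2.

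**Step 2: planning values.** b0 = 2.5 and the sum is 10 − 2.5 = 7.5 points. Participants offered the navigator per extra PrEP start = 100 / bN.

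| Split bN / bD / bT (points) | Control | Intervention | Per extra start, navigator |
|---|---|---|---|
| 7.5 / 0 / 0 | 2.5% | 10% | 100/7.5 = 13.3 |
| 2.5 / 2.5 / 2.5 | 2.5% | 10% | 100/2.5 = 40 |
| 0 / 7.5 / 0 | 2.5% | 10% | undefined |

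The trial data would be the same under all three rows. A navigator cost of C per participant would imply 13.3·C, 40·C or no finite cost per extra start. A larger sample would estimate the 7.5 more precisely and leave the split as open as before.

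**Step 3: is additivity safe?** If telehealth works mainly when a navigator makes the link, a navigator-by-telehealth term is needed. With all three main effects at 0 and that term at 7.5, intervention uptake is again 2.5 + 7.5 = 10%. The component effects then sum to 0, not 7.5. So additivity supplies the sum only if it is true, and never supplies the split. The exception in 10.4 concerns redundant costs, not effects that depend on each other.

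**Step 4: other Aim 1 data.** Section 9.2.4 records which elements participants use. That use is self-selected after randomisation, so comparing users with non-users would not give a randomised component effect. Phase 2 does not help either: 13.1 redeploys one refined intervention without randomisation.

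**The case against.** The strongest reply is that the plan's main economic analysis is not the one criticised. Section 10.4 defines the primary analysis as incremental cost per person started on PrEP, intervention against control, and the trial identifies that. Component costs come from micro-costing and time-and-motion records (10.2), so costs and budget impact by component are also measurable. All of this stands. A reader might infer that the Aim 2 base case as a whole is unsound, and the documents do not support that.

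Second, component combinations are already framed partly as assumptions. Section 10.1 varies costs and combined effectiveness in sensitivity analyses and draws on published PrEP data. Section 10.4 takes bounds from trial data, literature or expert opinion. This stands in part: it permits scenarios. It does not make component effects something Aim 1 assessed, and the plan names no specific source or method for a component's effect on uptake.

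Third, the output list in 10.5 gives only costs by component, and users can alter intervention effectiveness. It is therefore an inference, not a stated output, that the tool will print a cost per PrEP start for each component. The same section does commit to component cost-effectiveness results, so the risk remains.

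Fourth, a reader might conclude that telehealth cannot work at all without navigation. Section 3.2.1 says navigators can make the link, by self-referral, to existing outside services. It does not say they are the only route. The text supports doubt about additivity, not impossibility.

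**Conclusion.** The concern holds for component-level effectiveness and cost-effectiveness. The design identifies two quantities, control uptake and the package effect, and the promise in 10.1 needs at least four. At the planning values, one component's participants per extra start could be 13.3, 40 or undefined with identical trial results.

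The 13.3 should not be read as a floor, because it is a minimum only if the other components' effects do not sum to less than zero. A split of 10 / −2.5 / 0 also sums to 7.5 and would give 100/10 = 10. The identification result rests only on the two-arm bundled design. The illustrative figures also rest on the 9.1 planning values and on an additive scale.

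The trial's primary outcome, the primary package-versus-control ratio, and component costs and budget impact are untouched. No R61 milestone in Table 6 is a cost-effectiveness result. The wording should be corrected before the model and tool are built, but the trial's conclusions on PrEP uptake are not threatened.

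**What to change.** - **10.1:** remove the attribution of component effects to Aim 1.
- **10.1, 10.4 and 10.5:** restrict trial-based incremental cost-effectiveness ratios to the whole package against control. Keep reporting costs and budget impact by component.
- **10.4:** present component-level effectiveness and cost per PrEP start only as labelled scenario or threshold analyses, with the source and range of each assumed effect stated. Show non-additive scenarios (synergy, overlap, telehealth conditional on navigation) beside the additive one. Do not force component shares to sum to the package effect in every scenario, since that reimposes additivity.
- **10.5:** carry the scenario label into the decision tool wherever a component-level effect or ratio appears.

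No new data, arms or participants are needed. The cost is revised Aim 2 wording, some extra model runs, and fewer outputs that can be presented as trial evidence.

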10.2 Cost Measurement

We will embed an empirical costing study into Aim 1 activities. Costs will be collected prospectively in two ways: micro costing and time-and-motion logs. **Micro-costing** involves “direct enumeration” for consumed inputs⁵⁷, an ingredients-based approach. We will quantify resources associated with the development and implementation of our intervention (Table 5).

We will not assess fixed costs common to both arms (e.g., clinic operations overhead), or costs related to the conduct of the study alone (e.g., consent). Cost data will be available through contractual information with developers, clinic and project receipts, and NC DHHS supply chain partners. We will also extract data from project expenditure and management records, including purchase logs and human resource records. **Time-and-motion** assessments record how involved parties (navigators, providers, etc) divide time among PrEP-related tasks, reliably apportioning effort relevant to implementing the intervention. This includes time for: health worker trainings, PrEP navigators, and PrEP providers. Notably, PrEP provider costs will be estimated to inform clinics of the potential expenses (and possibly revenue) regardless of if a given clinic opts to implement PrEP programming during the study period. As such, costs of PrEP provision and monitoring may be extrapolated from available data even if these programs or activities are not uniformly implemented in participating STI clinics.

Table 5: Cost elements and data source

[figure not shown]
| Cost | Source |
|--------------------------|---|
| Trainings | Project receipts |
| HMP app updates | Project receipts |
| Telecommunications | Project receipts |
| Test supplies* | EHR |
| Healthcare utilization** | App paradata, EHR |
| Personnel | Time-and-motion, NC DHHS salary, project expenses |

*HIV, STI, renal function, **clinic visits

Costs will be calculated by multiplying total time spent with the average hourly salary of the respective roles for those who are only partially committed to PrEP services; persons whose roles are entirely PrEP-related (i.e. PrEP navigator) will be based on their 100% full time equivalent salary, with more in-depth exploration of distribution of time/tasks to examine opportunities to split service provision across multiple lower-volume health departments and other STI clinics. We will record this information in spreadsheets that document resource, category, quantity, and unit cost. We will follow international conventions for comprehensive costing (i.e. including equipment, consumables, and overhead that is not common to both arms); discounting future costs; and reporting based on accepted practices and guidelines from the Panel on Cost-Effectiveness in Health and Medicine⁵⁸. We will conduct sensitivity analyses that consider costs related to sustainability and intervention fidelity (e.g., monitoring and evaluation), varying intervention effectiveness with fidelity changes. Incorporating downstream costs is critical to adequately estimate costs of scale-up⁵⁹.

10.3 Model Design and Analytical Perspective

We will conduct decision analysis following best practices⁵⁷, moving a cohort through a decision tree (left-to-right), with the left-most decision node controlled by the randomized experiment in the trial (Fig 3). “Event nodes”, or probabilistic events that happen by chance, will be derived from trial data. Terminal node is PrEP uptake. We will assess cost-effectiveness outcomes from two perspectives: 1) the STI clinic; and 2) Medicaid or the state, grouped together because state governments cover a larger portion of Medicaid expenses and make decisions about Medicaid administration and public health programmatic offerings. We will assume that if Medicaid launched a version of our multilevel PrEP intervention, the materials, equipment, and personnel costs would be borne by Medicaid or its care coordination entity.

10.4 Outcomes and Analysis

We will conduct a budget impact analysis of the cost in dollars of the intervention overall and each of its components, answering the question of whether the intervention is *affordable* for an organization. We will also conduct a cost-effectiveness analysis estimating the incremental cost per additional person started on PrEP (the primary study outcome). We will run simulations to estimate additional costs and additional PrEP uptake compared to the status quo to assess whether the intervention provides *value* relative to the status quo. We will also assess cost per QALY gained, based on HIV infections averted, applying our estimates to accepted transmission models^{56,60}.

We will report incremental cost-effectiveness ratios (ICERs). Interventions that cost less and result in more PrEP starts, QALYs gained, or infections averted are cost-saving options. Interventions that cost more and result in more PrEP starts or more QALYs will be evaluated against standard willingness-to-pay thresholds (\$50,000, \$100,000, \$150,000 per QALY gained) contextualizing willingness to absorb costs per added QALY^{61,62}. For our primary outcome, for which willingness- to-pay thresholds are unavailable, we will plot outcomes on an efficiency frontier and cost-effectiveness acceptability curve to help decision makers visualize benefits gained at

different willingness-to-pay levels^{63,64}.

The budget impact analysis will provide decision makers with estimates of the financial feasibility of the intervention⁶⁴. We will examine the budget impact over 1- and 3-year time horizons. Budget impact analysis results will be particularly important for decision makers in healthcare systems, as they may not see the long-term benefits modeled in cost-effectiveness analyses due to individuals moving between clinics and insurance plans over the life course. For our primary analysis (incremental cost per person started on PrEP, comparing intervention to control arms), we will use a 1-year time horizon, aligning analyses with primary RCT **effectiveness** outcome (Aim 1).

Sensitivity analyses examine the potential impact of varying cost and effectiveness assumptions. We will employ deterministic sensitivity analyses to examine model assumptions and key parameter uncertainties. We will assume that intervention effects would be additive unless cost components are redundant. We will conduct probabilistic sensitivity analyses (using Monte Carlo simulation x5000) to account for parameter uncertainty⁶⁵, capturing input uncertainty (e.g., PrEP effectiveness, intervention cost and effectiveness). Upper and lower bounds will be based on trial data, literature, and/or expert opinion. Results represent an average across simulated model runs with an estimated uncertainty range. We will depict sensitivity results graphically and with relevant descriptive statistics. We will estimate net monetary benefits over a range of willingness-to-pay thresholds¹⁵⁵⁻¹⁵⁹, depicting the probability that each intervention is preferred given the decision maker is willing to pay at least the threshold value for each additional person started on PrEP or each QALY gained^{63,64,66,67}.

